### Power Analyses

Alcohol self-administration: Our previous alcohol self-administration work showed effect sizes from 0.49 to 1.31 according to the phenotype of interest. Neurophysiological correlates (EEG/fMRI): Published outcome and feedback-related differences in N200 and P300 amplitudes yield effect sizes from 0.78 to 2.12 for subjects with an AUD versus controls, and 0.62 to 1.6 for the effect of alcohol. There are no standards for power analyses in whole brain connectomics. However, our pilot data showed significant results in  $n=51$ , suggesting  $n=100$  is sufficient to find robust connectivity patterns. We will ensure robustness using permutation tests combined with an extent threshold, or alternatively, using the Permutation Network Framework. Relationship to AUD risk variables: In our pilot data, the relationship between SDA and AUD risk correlates ranged from  $r=0.32 - 0.63$ . With a sample of  $n=100$ , we can detect an effect size of at least 0.32 and still maintain adequate  $power=0.90$ ,  $\alpha=0.01$ . When categorized by groups of  $n=50$  (high/low lifetime drinking history), we can detect differences with an effect size of 0.64 and still maintain adequate  $power=0.90$ ,  $\alpha=0.01$ .

Supplemental and Exploratory analyses. Our careful experimental design allows for exploratory analyses in many domains including, but not limited to, comparing and contrasting the relationships between SDA, lifetime drinking history and other descriptive variables of interest including AUDIT, age of drinking onset, the DSM 5 symptom most reflective of aversion-resistance, nicotine history, stop signal task behavioral and electrophysiological response, and the PTSD screening results. We will explore the relationship between SDA and the *intensity* and *timing* of alcohol exposure – e.g. does elevated drinking during late adolescence/early adulthood have stronger relationship with SDA than either consistent low-level drinking over a longer time period or intense drinking later in life. We may also pursue structural brain alterations that may be associated with SDA or alternative connectivity analyses and interactions with smoking. We will explore differences in baseline feedback-related ERPs and stop signal task behavioral and electrophysiologic indices as a function of session type and order. We will also examine differences across men and women, including menstrual phase, as our previous data does suggest gender moderation in the effects of mood induction and post-abstinence response on alcohol self-administration. Finally, with consent, we are collecting blood samples to allow for the combination of data from this project with previous IARC human samples; enabling future analysis of polygenic risk in this sample.

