#### 4.0 Enrollment/Randomization

The project employs a between-participants design. Each participant will undertake 3 or 4 sessions: an interview/screening session, 2 randomly counter-balanced (neutral and aversive stimuli) IV alcohol self-administration sessions, and in a subset of subjects that meet the criteria outlined in the fMRI screen, an fMRI resting state scan. All sessions will take place in the Neural Systems Laboratory at the Indiana Clinical Research Center at Indiana University Hospital or at the Neuroscience Center at Methodist Hospital.

We will consent 300 participants to enroll 150 and complete 100 participants: **a**) 50 individuals who are current drinkers with lower lifetime drinking history, between 25-50 kg ethanol, **b**) 50 individuals who are heavy drinkers with a higher lifetime drinking history of 250-500 kg ethanol, and **c**) individuals below 500 kg ethanol at the discretion of the principle investigator. We will target equal numbers of men and women for inclusion in the lower and higher lifetime drinking groups. Total participant payment will be \$400, plus parking/travel costs.

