#### Aim 2 Hypothesis Testing Plan.

**Hypothesis 3:** Those with greater SDA will have greater AUD severity, greater LDH, greater negative urgency, greater density of familial history of alcoholism, and reduced subjective, behavioral, and electrophysiologic sensitivity to alcohol. To minimize error inflation from multiple univariate tests, we will use structural equation modeling (R3.01 data analysis software using the lavaan statistical package; Figure 6). We will examine AUD severity as an observed independent variable of AUD symptom count. Lifetime Drinking History and density of family history of alcoholism will be observed variables, computed with information collected with Concordia Lifetime Drinking Questionnaire and the SSAGA family history module. Negative urgency will be defined as a latent independent variable, with individual item indicators from the UPPS-P negative urgency subscale. Sensitivity to alcohol will be defined as a latent independent variable with three measured variable predictors: Subjective, behavioral and electrophysiological sensitivity to 60mg/dl alcohol as compared to each individual's baseline response. The dependent measures of interest for sensitivity analysis include Subjective Response to Alcohol, Wisconsin Card Sort, and the Stop Signal Task. The dependent variable will be cumulative work performed for alcohol in the aversive session, defined as an observed variable. We will control for cumulative work performed for alcohol in the neutral session, as well as age, gender, and race, due to their relationship with alcohol use behaviors. Judgment of hypothesis viability will be assessed via **1**) fit indices (recommendations in parentheses: Root Mean Square Error of Approximation ( $RMSEA < 0.10$ ); Tucker Lewis Index ( $TLI > 0.95$ ); and Comparative Fit Index ( $CFI > 0.95$ ) and **2**) pathway loading significance.

**Hypothesis 4:** Significant factors from hypothesis 3 can identify a latent trait that classifies individuals into at two classes of individuals: those who have high and low SDA. The significant phenotypes from hypothesis 3 will be used in a latent class analysis to identify subgroups based on

**Figure 6. Proposed path analysis.** Covariates, error terms, and correlations not shown for simplicity

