***Hypothesis 6a:*** *Those with greater SDA will demonstrate greater resting state crosstalk (less differentiation) between the default mode and fronto-parietal networks.* Our preliminary results (Figure 5, above) suggest that advancing AUD severity increases communication between networks that are functionally independent (i.e., the default mode network is prominent at rest, while the fronto-parietal network is activated by focused mental activity). As we hypothesize that SDA marks increasing AUD severity, we similarly hypothesize that SDA is related to abnormally increased communication between the default mode and fronto-parietal networks. To test this hypothesis, whole-brain functional connectivity (FC) will be estimated for each individual participant using a data-driven, functionally based parcellation and characterized for segregation/modularity, which reflects the underlying organization into functional modules or communities. Age will be a covariate in all analyses. Furthermore, to characterize the tendency of brain regions to belong to the same module as a fine-grain continuum (as opposed to an integral membership), we use the consensus clustering approach. The pairwise correlations between module consensus and SDA of participants represent a mapping of SDA into the functional connectome domain. To control for false positives, the correlation between segregation/modularity (consensus clustering approach) and SDA will be z-normalized using 10,000 permutation tests, where the SDA vectors will be randomly shuffled and their associations with modularity consensus mapped 10,000 times, producing a distribution of expected SDA associations by chance. Based on the mean and standard deviation of this null distribution, the actual SDA associations can be z-scored and thresholded at  $p < 0.05$  (equivalent to a two tailed, i.e.,  $|z| > 1.96$ , for significant associations). To minimize false positives, we will also incorporate the equivalent of an extent threshold for network-based associations to account for the effect size (as measured by number of edges in connected components or by their spatial pairwise clustering) of the associations in the functional connectome domain. We will also consider using the Permutation Network Framework (PNF), which makes no assumptions about the distribution of the test statistics, since they often show non-standard distributions due to the intrinsic complex nature of brain connectivity data. To evaluate the robustness and reproducibility of these results, other gray matter parcellation schemes will also be assessed, using atlases that range from coarser to finer resolutions (from anatomically-based with 84 regions to multimodal with 360 regions, respectively). Using a similar approach, we will evaluate the associations between SDA and the network properties of integration and centrality. Integration reflects communication efficiency, often reflected by distance to closure

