
transformations of the shortest-path-lengths between nodes. Centrality measurements rank the relevant brain regions based on how central the nodes are and cover communicability aspects such as degree (number of edges per region) or the number of shortest-paths through each region (betweenness centrality).

**Hypothesis 6b:** *Those with greater SDA will demonstrate reduced ventral striatal-ventromedial frontal connectivity.* We will complement the connectome approach by using a seed-based approach to test voxel-level functional connectivity between the ventral striatum and ventromedial prefrontal cortex and its relation to SDA. For each subject, the functional connectivity between the ventral striatal seed (Figure 7d, red seed region) and all other cerebral gray matter voxels will be computed and transformed to MNI standard space for each subject. Age will be a covariate in all analyses. Finally, the resulting ventral striatal seed-to-gray-matter voxel-level FC estimations will be correlated (Pearson's coefficient) with subjects' SDA, yielding a high resolution (voxel-level) mapping of SDA onto fronto-striatal connectivity patterns. To control false positive findings, a multiple comparison correction based on false discovery rate will be applied ( $p_{FDR} < 0.05$ ) with an extent threshold ( $k=50$ ) to avoid spurious isolated voxels and small clusters.

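### The stated power of 0.90 and alpha of 0.01 do not fit either planning effect as a simple test; both effects fit two-sided alpha of about 0.05

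*Combined protocol and SAP*

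**What the plan says.** Section 7.0, Power Analyses, reports that in pilot data "the relationship between SDA and AUD risk correlates ranged from" r=0.32 to 0.63. It then says that with n=100 "we can detect an effect size of at least 0.32 and still maintain adequate" power of 0.90 at alpha 0.01. For the high and low lifetime-drinking groups of 50 each, "we can detect differences with an effect size of 0.64 and still maintain adequate" the same power at the same alpha. No sidedness, formula, software or effect metric is given for either figure.

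Other places in the documents bear on the alpha:

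- Hypothesis 6a: "the actual SDA associations can be z-scored and thresholded at" p<0.05, given as equivalent to |z|>1.96, two-tailed.
- Hypothesis 6b: "a multiple comparison correction based on false discovery rate will be applied" at 0.05.
- Hypothesis 3: "To minimize error inflation from multiple univariate tests, we will use structural equation modeling", with no alpha for the path tests.
- Hypotheses 1, 2, 4 and 5: no alpha.

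On imaging, Power Analyses says that n=100 "is sufficient to find robust connectivity patterns". Section 4.0 plans 100 completers and provides, "in a subset of subjects that meet the criteria outlined in the fMRI screen, an fMRI resting state scan". Section 5.0 (Screening) likewise refers to a subset for the fMRI sessions.

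**The concern.** Alpha, power, sample size and effect size are tied together: fixing any three determines the fourth. Here all four are printed, for two designs, and in neither do they agree.

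The value 0.32 is the bottom of the pilot range, so this sentence is the plan's support for detecting the weaker risk correlates. It also gives the only alpha a reader could apply to Hypotheses 1 to 5. A reader who takes 0.01 at face value would think a strict level had been adopted and still carried 0.90 power. If the level is really 0.05, no such strictness was budgeted for. If it is really 0.01, the power is overstated.

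The connectivity sentence raises a smaller, separate point. It rests on all 100 completers, while the procedures scan only some of them.

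**Working it through.** **Inputs (Power Analyses, unless noted)**

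- Correlation: 0.32, n=100. I read 0.32 as r because it equals the lower end of the pilot range given in r one sentence before.
- Group comparison: 0.64, 50 per group. I read 0.64 as a standardized mean difference d; the plan does not label it.
- Stated power 0.90 and alpha 0.01 for both. Sidedness is not stated, so both were tried.
- No dropout adjustment is needed: Section 4.0 gives 100 as the number of completers.

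**Correlation, Fisher z**

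Power = Φ(atanh(r)·√(n−3) − z).

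atanh(0.32)·√97 = 0.3316 × 9.849 = 3.266.

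| Alpha | z | 3.266 − z | Power |
|---|---|---|---|
| 0.01 two-sided | 2.576 | 0.690 | 0.755 |
| 0.01 one-sided | 2.326 | 0.940 | 0.826 |
| 0.05 two-sided | 1.960 | 1.306 | 0.904 |

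Simulating bivariate normal samples of 100 with the t test of r gives 0.757 at two-sided 0.01 and about 0.906 at two-sided 0.05.

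**Two groups, noncentral t**

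df = 98; noncentrality = d·√(n/2) = 0.64 × √25 = 3.2.

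| Alpha | Critical t | Power |
|---|---|---|
| 0.01 two-sided | 2.627 | 0.716 |
| 0.01 one-sided | 2.365 | 0.797 |
| 0.05 two-sided | 1.984 | 0.887 |

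The normal approximation gives 0.734, 0.809 and 0.893.

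The plan's 0.90 is therefore not reproduced at alpha 0.01 in any of these rows. At two-sided 0.05 both figures are within two percentage points of it.

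**Solving for the other quantities**

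- Two-sided alpha that gives exactly 0.90 power: 0.047 for r=0.32 and 0.059 for d=0.64 (0.055 by the normal approximation). That is about five to six times the stated 0.01.
- Effects detectable at two-sided 0.05 with 0.90 power: r=0.318 and d=0.655, close to the printed 0.32 and 0.64.
- Effects detectable at two-sided 0.01 with 0.90 power: r = tanh((2.576+1.282)/√97) = 0.373 and d=0.785. To two decimals, r=0.37 has power 0.894 and r=0.38 has 0.914; d=0.78 has 0.896 and d=0.79 has 0.904.
- Sizes needed to keep 0.32, 0.64, two-sided 0.01 and 0.90 power: about 139 in total and 75 per group.

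**Other readings of 0.32**

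Taken as Cohen's f or a one-sample d, it gives power 0.716 at two-sided 0.01 and 0.887 at 0.05, which leads to the same conclusion. Taken as f-squared, it gives about 0.98 or more at 0.01 (one to five predictors), which overshoots 0.90.

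**Connectivity**

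No power can be computed. The documents give neither the size of the scanned subset nor a connectivity effect size.

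**The case against.** The arithmetic is not in dispute. The best case for the plan is that its analyses are not simple tests. Hypotheses 1 and 2 use covariate-adjusted mixed models, Hypothesis 2 has two repeated measures, and Hypothesis 3 is a structural equation model. Under such models, 0.90 at two-sided 0.01 is reachable. With d=0.64 averaged over two sessions, power is 0.908 if the between-session correlation is 0.3, 0.855 at 0.5 and 0.770 at 0.8. With 0.32 as a semi-partial correlation, power is 0.882 if covariates explain 20% of the outcome variance and 0.908 at 25%. These inputs are assumptions, however. The plan states none of them, and covariates correlated with lifetime drinking could lower power. They show what could have been done, not what the paragraph supports. What stands is the scope: the failure to reproduce applies to simple bivariate and two-sample calculations.

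A second objection is that the misstated item need not be alpha. One-sided 0.01 with power 0.80 fits d=0.64 (0.797), though it fits r=0.32 less well (0.826). The value 0.01 is printed twice, and Hypothesis 3 shows awareness of error inflation, so a deliberate 0.01 is conceivable. The 0.05 thresholds for Hypotheses 6a and 6b belong to connectivity mapping and say little about the risk correlates. This stands as a limit on the diagnosis. Two-sided 0.05 fits the pair better, but it remains an inference.

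Third, the practical loss may be small. Even at two-sided 0.01, r=0.40 has power 0.945, so the correlation shortfall is confined to the lower end of the pilot range. That is correct and bears on the weight of the point, not on whether the sentence is wrong.

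On connectivity, the procedures give no number scanned, the pilot found significant results at n=51, and the plan itself says no power standard exists. So only the mismatch between 100 and a subset can be asserted.

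**Conclusion.** The concern holds. Reading 0.32 as r and 0.64 as a standardized mean difference, and using simple tests, the design does not deliver 0.90 power at the stated alpha. It delivers 0.755 and 0.716 two-sided, or 0.826 and 0.797 one-sided. At the two-sided level, the chance of missing these effects is about 24% (1 − 0.755) and 28% (1 − 0.716), against the 10% implied.

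The alpha is probably the misprint, since two-sided 0.05 nearly restores both claims. In that case the sample is adequate much as claimed. The inconsistency itself is certain under these readings; which term is wrong is for the sponsor to say.

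The connectivity sentence quotes a number that does not match the procedures, with an effect on power that cannot be quantified. This should be fixed, but it does not call the design into question.

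**What to change.** Restate the paragraph without changing the sample.

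1. Choose one version and state the sidedness:
   - (a) two-sided alpha 0.05, with power 0.90 at r=0.32 and 0.89 at d=0.64; or
   - (b) two-sided alpha 0.01, with power 0.76 and 0.72 at those effects, or equivalently detectable effects of r=0.38 and d=0.79 at 0.90 power.
2. Label 0.32 as a correlation and 0.64 as a standardized mean difference, or name the metric actually used.
3. Say that these are simple bivariate and two-sample calculations, not power for the adjusted mixed models or the structural equation model. If another method was used, give it with its inputs.
4. State the same alpha for the tests of Hypotheses 1 to 5.
5. In the connectivity sentence, replace n=100 with the number expected to be scanned.

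The cost is wording only. Under (a) the claims barely change. Under (b) the stated figures become less favourable.

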## **7.0 Statistical Considerations**

### **Aim 1: Characterize SDA across lifetime drinking history.**

#### Aim 1 Hypothesis Testing Plan

[figure not shown]
*Hypothesis 1: Greater SDA will reflect greater lifetime drinking.* We will conduct a linear mixed-model analysis, with lifetime drinking history as the continuous independent variable and with SDA as the dependent variable. Lifetime drinking history will be defined as the kg of alcohol reported consumed via the Concordia Lifetime Drinking Questionnaire. SDA will be defined as the amount of work performed (cumulative number of SDA trials completed) for alcohol rewards in the aversive session. Age, gender, recent drinking history, and race will be included as covariates, due to their relationship with AUDs.

**Hypothesis 2:** Those with a high lifetime drinking history will demonstrate less sensitivity to aversion in the preference to work for alcohol. Specifically, those with a high lifetime drinking history will work more for alcohol compared to water under both neutral and aversive conditions, whereas those with a low lifetime drinking history will only work more for alcohol compared to water in the neutral session. We will conduct a mixed linear model in which lifetime drinking history is the independent variable, as in hypothesis 1, but using a different dependent measure. We will subtract work for water from work for alcohol, dividing the difference by the sum of the work done for alcohol plus water (separately under the aversive stimulus ( $R_a$ ) and under the neutral stimulus ( $R_n$ )). The ratios  $R_a$  and  $R_n$  will be used as the repeated measures dependent variables, and lifetime drinking history (high vs. low), stimulus type (aversive vs. neutral) and their interaction will be independent variables. Covariates will include age, gender, recent drinking history, and race. If lifetime drinking history and the interaction with stimulus are significant predictors of the ratios of work performed, we will conduct follow-up planned contrasts to examine the ratios separately for the neutral and aversive sessions to test high and low lifetime drinking history.

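### The 50-per-group power figure (effect 0.64, power 0.90, alpha 0.01) does not agree with itself, and no power is given for Hypothesis 2's interaction or its two-part condition

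*Combined protocol and SAP*

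**What the plan says.** Section 7.0, Power Analyses, has one statement about the high/low groups: "When categorized by groups of $n=50$ (high/low lifetime drinking history), we can detect differences with an effect size of 0.64", with power 0.90 and alpha 0.01. It names no hypothesis, outcome, session or sidedness.

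The groups come from section 4.0, which plans for "50 individuals who are heavy drinkers with a higher lifetime drinking history of 250-500 kg ethanol" and 50 with a lower history (25-50 kg). One hundred is the completer target: "We will consent 300 participants to enroll 150 and complete 100 participants".

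Among the numbered hypotheses, only H2 (section 7.0, Aim 1 Hypothesis Testing Plan) splits LDH into high and low. It forms a relative preference for alcohol over water in each session, Ra (aversive) and Rn (neutral), and analyses the two as repeated measures on each participant. The model terms are given as follows: "lifetime drinking history (high vs. low), stimulus type (aversive vs. neutral) and their interaction will be independent variables". The next step is conditional: "If lifetime drinking history and the interaction with stimulus are significant predictors of the ratios of work performed, we will conduct follow-up planned contrasts" by session. Age, gender, recent drinking and race are covariates. The correlation between Ra and Rn is not given.

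**The concern.** There are two separate problems. First, effect size, group size, power and alpha are tied together by a formula, and the four printed values do not fit it for a two-group comparison. Second, even a corrected two-group figure would not be the power of H2. H2 rests on two other quantities: the group difference in the average of Ra and Rn, and the group difference in Ra − Rn. A gap confined to one session is halved in the average, while the interaction is scaled by the SD of a within-person difference. The plan needs both to be significant before it looks at the sessions separately.

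At stake is how a non-significant result is read. If the condition is not met, a reader could take that as evidence against reduced sensitivity to aversion from a study described as having 90% power. No such power has been shown for this analysis.

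**Working it through.** **Inputs.** From Power Analyses: 50 per group, effect 0.64 (read as a standardised mean difference), power 0.90, alpha 0.01, prior self-administration effects of 0.49 to 1.31. From H2: two measures per person and the two-part condition. Assumed, because not stated: two-sided tests, equal SDs, no covariates, correlation ρ of Ra and Rn between 0 and 0.9, and the size of the group gap in each session.

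**Step 1: the plan's own figure.** For a two-sample t-test with 50 per group, df = 98 and the noncentrality is d × √(50/2) = 5d. At d = 0.64 this is 3.2.

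- Two-sided alpha 0.05 (critical t 1.984): power 0.887.
- Two-sided alpha 0.01 (critical t 2.627): power 0.716.
- One-sided alpha 0.01: power 0.797.

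So 0.90 is approached at two-sided 0.05, not at the printed 0.01. At two-sided 0.01 and power 0.90 the detectable effect is about 0.78. The companion correlation figure (r = 0.32, n = 100) behaves the same way: 0.755 at two-sided 0.01 and 0.904 at 0.05.

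**Step 2: H2's two tests.** Let da and dn be the group gaps in the aversive and neutral sessions, in single-session SD units.

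- LDH effect averaged over sessions: d_main = ((da + dn)/2) / √((1 + ρ)/2)
- LDH × stimulus interaction: d_int = (da − dn) / √(2(1 − ρ))

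With equal variances the sum and difference of Ra and Rn are uncorrelated, so joint power is the product of the two powers.

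**Step 3: illustration with da = 0.64, dn = 0.**

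| ρ | d_main | d_int | Main / interaction / both, alpha 0.05 | Main / interaction / both, alpha 0.01 |
|---|---|---|---|---|
| 0 | 0.453 | 0.453 | 0.61 / 0.61 / 0.37 | 0.36 / 0.36 / 0.13 |
| 0.5 | 0.370 | 0.640 | 0.45 / 0.89 / 0.40 | 0.22 / 0.72 / 0.16 |
| 0.8 | 0.337 | 1.012 | 0.39 / 1.00 / 0.39 | 0.18 / 0.99 / 0.18 |
| 0.9 | 0.328 | 1.431 | 0.37 / 1.00 / 0.37 | 0.17 / 1.00 / 0.17 |

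Simulation (10,000 runs per setting) agrees: 0.37, 0.39, 0.39 at alpha 0.05 and 0.13, 0.16, 0.17 at alpha 0.01, for ρ = 0, 0.5, 0.8.

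**Step 4: how far this depends on the assumptions** (alpha 0.05 unless stated).

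- Neutral-session gap of 0.1 to 0.4 SD, ρ 0 to 0.9: both significant 0.13 to 0.64.
- LDH effect coded as the aversive-session gap (da = 0.64, dn = 0): simulated joint power is 0.60, 0.82 and 0.89 at ρ = 0, 0.5, 0.8.
- 0.64 taken as the standardised effect of each test on its own scale: 0.887 × 0.887 = 0.79 (0.716 × 0.716 = 0.51 at alpha 0.01).
- Gap in the aversive session only, session-averaged coding, other sizes: 0.16 to 0.24 at da = 0.49 and 0.91 to 0.99 at da = 1.31 (0.77 to 0.95 at alpha 0.01). Joint power of 0.90 needs da of about 1.03 to 1.28.

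**Step 5: detectable interaction** (da − dn) at power 0.90, unadjusted. Multiply the detectable two-sample effect, 0.65 at alpha 0.05 or 0.78 at 0.01, by √(2(1 − ρ)). For ρ = 0 / 0.5 / 0.8 this gives about 0.93 / 0.65 / 0.41 at alpha 0.05 and 1.11 / 0.78 / 0.50 at alpha 0.01.

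**The case against.** The strongest reply is that the power section never ties 0.64 to H2, to Ra and Rn, or to the aversive session. It is offered as a detectable difference, not a planned one. H2 says that both groups prefer alcohol in the neutral session; it does not say that they prefer it equally, so a neutral gap of zero is a reviewer's choice. The H2 text first refers to LDH as in Hypothesis 1 (continuous) and then as high versus low, and it does not define how the LDH effect is coded. Covariates could raise power by explaining outcome variance, or lower it by overlapping with LDH. All of this stands, and it limits what the illustration can show.

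A reader might therefore be tempted to infer that H2 has only about a 0.4 chance of success, or will more often than not fail. The documents do not support that. The value needs alpha 0.05, an aversive-only gap of 0.64 and a session-averaged LDH effect, none of which the plan fixes for H2. Nor does the plan say that H2 is rejected when the condition is not met; it says only when the contrasts follow.

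It is also not true that the main-effect condition is always the obstacle. With a neutral gap of 0.32 and ρ = 0, main-effect power is 0.92, interaction power 0.20 and joint power 0.19, so dropping the condition gains almost nothing.

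One two-group variant does give about 0.90 at alpha 0.01: a two-session mean with gaps of 0.64 in both sessions and ρ about 0.3 to 0.4 (0.91 to 0.88). The plan states no such inputs, and equal gaps mean no interaction, so this cannot support H2.

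None of these points reconciles the printed alpha with the printed power for a single-measure comparison, or supplies a power for the interaction.

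**Conclusion.** The concern holds in two parts. The first needs only the reading of 0.64 as a standardised difference in a single-measure, two-sided comparison: power is 0.72 at the printed alpha, not 0.90. The second is an omission that is plain from the text: H2's interaction and its two-part condition have no stated power, and the two-group figure cannot stand in for them.

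The size of the second shortfall is conditional. With session-averaged coding, joint power at a gap of 0.64 stays well below 0.90 for all the neutral gaps examined, and becomes adequate only towards the top of the prior effect range. With aversive-session coding and a high correlation it comes close to 0.90 at alpha 0.05. The documents do not settle which case applies, so they do not show that 100 completers are too few for H2.

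**What to change.** 1. In Power Analyses, make alpha and power agree: either alpha 0.05 with power about 0.89 at 0.64, or alpha 0.01 with power about 0.72 at 0.64 (or a detectable effect of about 0.78). Say that the figure is for a two-group comparison of a single measure. The correlation sentence beside it needs the same reconciliation.
2. Add the detectable LDH × stimulus interaction for H2 at the chosen alpha, using the correlation of Ra and Rn from the pilot. The Step 5 values show the range to expect.
3. In H2, let the interaction decide whether high-LDH participants are less sensitive to aversion, since that is the contrast the phrase describes, and let it trigger the session contrasts. Report the LDH main effect without making it a condition.

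The cost is rewording two paragraphs and a short calculation from pilot data, with no extra participants or procedures. The downside is a less favourable stated power. How much item 3 gains depends on the neutral-session gap and ρ: at dn = 0 and ρ = 0.5 (alpha 0.05), power goes from 0.40 for both tests to 0.89 for the interaction alone, but the gain is small where the interaction is the limiting test.
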